#### 1.4.3.5 Risk minimization (safety precautions and stopping rules)

The following risk minimization measures, including safety precautions and stopping rules, will be implemented in this study:

- Careful selection of starting dose, as described in [Section 1.3.1](#).
- Decreasing escalation factors with increasing doses, as described in [Section 1.3.2](#). Dose escalations will only be allowed after documented interim safety reviews (see [Section 3.1.1](#)).
- Preliminary measurement of BI 764122 pharmacokinetics ( $C_{max}$ ,  $AUC_{0-24}$ ; see [Section 7.3.2](#)). The expected exposure in the next higher DG will be estimated based on preliminary PK data of preceding DGs. The next higher dose level will only be administered, if estimated mean values of  $C_{max}$  and  $AUC_{0-24}$  do not exceed the maximum acceptable human exposure (see [Section 1.3.2](#)).
- For safety reasons, division of each DG of 8 subjects (6 on active treatment, 2 on placebo) into 3 staggered cohorts. On the first study day of each dose level, 2 subjects (Cohort 1) will be treated (one with active treatment, the other with placebo). On the second study day, the next 2 subjects (Cohort 2) will be treated (two with active

Proprietary confidential information © 2019 Boehringer Ingelheim International GmbH or one or more of its affiliated companies

treatment). On the third study day of each dose level, the remaining 4 subjects (Cohort 3) will be treated (three with active treatment, one with placebo). If BI 764122 was safe and well tolerated in Cohort 1, the study will continue with Cohort 2. If it was safe and well tolerated in the preceding cohorts, the study will continue with Cohort 3. Between the first application of BI 764122 in each cohort, there will be a time interval of at least 24 h which is expected to cover the peak exposure of the compound. In Cohort 2 and 3, subjects will be dosed at least 1 hour apart.

- A monitoring of safety laboratory with specific focus on glycemic control, hepatic- and hematological integrity (see [Flow Chart](#)).
- An ECG monitoring including continuous ECG measurement over 4 hours post dose to cover the anticipated period of highest drug exposure and additional repeated single or triplicate 12-lead ECGs over 72 hours following drug administration. Dose escalation would be stopped as soon as at least 2 subjects at one dose level showed relevant QT prolongation (see [Section 3.3.4.3](#)).

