#### **4.1.5 Blinding and procedures for unblinding**

##### **4.1.5.1 Blinding**

The SRD part of the trial is designed single-blind. The treatments administered (active or placebo) will be blinded to subjects but will be known to the investigators (outcome assessors). Only the current dose level will be known to the subjects due to the rising dose design. This is considered acceptable because the potential bias in this type of study seems to be low, and according to study procedures, it is assured that the investigator's knowledge of the next treatment does not influence the decision to enter a subject.

The FE part of the trial will be handled in an open fashion throughout (that is, during the conduct, including data cleaning and preparation of the analysis). This is considered acceptable because the potential for bias seems to be low and does not outweigh practical considerations.

All trial data will be handled open label. This means that trial functions of the sponsor are unblinded (e.g. clinical trial lead, data manager, statistician, bioanalyst, pharmacokineticist, pharmacometrist, drug metabolism scientist as well as dedicated personnel of the trial site).

Within the central ECG lab, the staff involved with interval measurements will be blinded with respect to the treatment and also with regard to the recording date and time as well as planned time points of the ECGs. The interval measurements for a given subject will be performed in a random and blinded sequence by a single technician. No more than two different blinded readers will evaluate the ECGs of the study.

Access to the randomisation schedule will be controlled and documented by a signed confidentiality statement, which will be stored in the TMF.

Proprietary confidential information © 2019 Boehringer Ingelheim International GmbH or one or more of its affiliated companies

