**5.2.6      Assessment of adverse events**

**5.2.6.1      Definitions of adverse events**

**5.2.6.1.1      Adverse event**

An adverse event (AE) is defined as any untoward medical occurrence in a patient or clinical investigation subject administered a medicinal product and which does not necessarily have to have a causal relationship with this treatment.

Proprietary confidential information © 2019 Boehringer Ingelheim International GmbH or one or more of its affiliated companies

An AE can therefore be any unfavourable and unintended sign (including an abnormal laboratory finding), symptom, or disease temporally associated with the use of a medicinal product, whether or not considered related to the medicinal product.

The following should also be recorded as an AE in the CRF and BI SAE form (if applicable):

- Worsening of the underlying disease or of other pre-existing conditions
- Changes in vital signs, ECG, physical examination, and laboratory test results, if they are judged clinically relevant by the investigator

If such abnormalities already pre-exist prior to trial inclusion, they will be considered as baseline conditions and should be collected in the eCRF only.

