7.8.1 Adverse events

AEs will be coded with the most recent version of MedDRA.

The analyses of AEs will be descriptive in nature. All analyses of AEs will be based on the number of subjects with AEs and not on the number of AEs.

For analysis, multiple AE occurrence data on the electronic case report form (eCRF) will be collapsed into an AE event provided that all of the following applies:

- All AE attributes are identical (LLT, intensity, action taken, therapy required, seriousness, reason for seriousness, relationship, outcome, AESI)
- The occurrences were time-overlapping or time-adjacent (time-adjacency of two occurrences is given if the second occurrence started at most 1 hour after the first occurrence ended).

For further details on summarization of AE data, please refer to "Analysis and presentation of adverse event data from Clinical Trials" (7) and "Handling of missing and incomplete AE dates" (3).

The analysis of AEs will be based on the concept of treatment emergent AEs. That means that all AEs will be assigned to the screening or treatment phases as defined in [Section 6.1](#). AEs will be analysed based on actual treatments, as defined in [Table 6.1: 1](#).

An overall summary of AEs will be presented. This overall summary will comprise summary statistics for the class of other significant AEs according to ICH E3 (8) and for the class of AESIs.

CTP: Hepatic injury

A hepatic injury is defined by the following alterations of hepatic laboratory parameters::

- *An elevation of AST (aspartate transaminase) and/or ALT (alanine transaminase) ≥ 3 -fold ULN combined with an elevation of total bilirubin ≥ 2 -fold ULN measured in the same blood sample, or*
- *Aminotransferase (ALT, and/or AST) elevations ≥ 10 fold ULN*

The investigator had to classify on the eCRF whether an observed AE was an AESI or not.

According to ICH E3 (8), AEs classified as 'other significant' need to be reported and will include those non-serious and non-significant AEs

- (i) which are marked haematological or other lab abnormalities, or
- (ii) which were reported with 'action taken = discontinuation' or 'action taken = reduced', or
- (iii) which lead to significant concomitant therapy as identified by the Clinical Monitor/Investigator at a Medical Quality Review Meeting.

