7.8.2 Laboratory data

The analyses of laboratory data will be descriptive in nature and will be based on BI standard "Display and Analysis of Laboratory Data" ([9](#)).

Analyses will be based on normalised values, which means transforming to a standard unit and a standard reference range.

Descriptive statistics of laboratory values over time and for the difference from baseline (see [Section 6.7](#)) will be provided. Frequency tables of changes between baseline and last value on treatment with respect to the reference range will be presented.

Possibly clinically significant abnormal laboratory values are only those identified either in the Investigator's comments on the eCRF or at the RPM at the latest. It is the Investigator's responsibility to decide whether a lab value is clinically significant abnormal or not. Standard or project-specific rules for flagging clinically significant values will not be applied in this study.

Clinically relevant findings in laboratory data will be reported as AEs and will be analysed as part of AE analysis.

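### The SAP plans no judgement-free count of marked laboratory abnormalities by dose against pooled placebo, and describes no check of the hepatic AESI against the laboratory data

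*SAP*

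**What the plan says.** SAP 7.8.2 fixes the source of the flag: "Possibly clinically significant abnormal laboratory values are only those identified either in the Investigator's comments on the eCRF or at the RPM at the latest". The same section places the decision with one role ("It is the Investigator's responsibility to decide whether a lab value is clinically significant abnormal or not") and closes the alternative route: "Standard or project-specific rules for flagging clinically significant values will not be applied in this study". Findings judged clinically relevant are then analysed as AEs.

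SAP 7.8.1 repeats the protocol's numeric definition of the hepatic AESI: "A hepatic injury is defined by the following alterations of hepatic laboratory parameters". The criteria are AST and/or ALT at least 3-fold ULN with total bilirubin at least 2-fold ULN in one sample, or ALT and/or AST at least 10-fold ULN. For the analysis, however, the stated source is a classification: "The investigator had to classify on the eCRF whether an observed AE was an AESI or not". No derivation from the laboratory data is described.

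Protocol 5.2.6.1.1 admits to the AE record "Changes in vital signs, ECG, physical examination, and laboratory test results, if they are judged clinically relevant by the investigator". Protocol 4.1.5.1 says that SRD treatments "will be blinded to subjects but will be known to the investigators (outcome assessors", that sponsor functions (among them the data manager and the statistician) are unblinded, and that the FE part is open.

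**The concern.** A laboratory value is a measurement, but whether it counts as clinically significant is here an opinion held by people who know the treatment. The same rise in ALT could be read differently at 400 mg and on placebo. The direction of such a bias cannot be predicted, and without a fixed threshold its size cannot be checked afterwards.

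This matters because laboratory safety is where the protocol expects a signal. Section 1.4.3.5 lists among its safety measures "A monitoring of safety laboratory with specific focus on glycemic control, hepatic- and hematological integrity". Section 1.3.2 bases the exposure limit on the dog NOEL rather than the NOAEL because of an ALT increase that did not reverse and a reversible decrease in thymus size. At stake is the comparison of each dose with pooled placebo on these findings. The same judgement decides which laboratory changes enter the AE tables, and so which can reach the primary endpoint of drug-related AEs.

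**Working it through.** The plan gives no figure to reproduce on this point. The check sets the provisions side by side and then sizes the effect of one classification.

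**1. Which displays need a judgement?**

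| Display | Source | Judgement needed? | Limit |
|---|---|---|---|
| Out-of-range values highlighted in listings | Protocol 7.3.4 | No | Not a frequency by group |
| Individual values listed | SAP 7 | No | Not a frequency by group |
| Mean, SD, min, median, max over time | SAP 7 and 7.8.2 | No | Shows the extreme value, not how many subjects passed a threshold |
| Reference-range shift table | SAP 7.8.2 | No | Final on-treatment value only; a value just above ULN and a large multiple of ULN share a category |
| Clinically significant values | SAP 7.8.2 | Yes | No fixed criterion |
| 'Other significant' AEs with marked laboratory abnormality | SAP 7.8.1 | Yes | No criterion for 'marked' |
| Hepatic AESI table | SAP 7.8.1 | Numeric definition, but the source is the investigator's classification | No check against laboratory data described |

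**2. What can the shift table miss?** Protocol Table 5.2.3: 1 schedules haematology and liver enzymes at 4, 24, 48 and 96 h, and at the end-of-trial visit (Days 7 to 11). SAP Table 6.1: 1 ends the SRD on-treatment phase at 7 × 24 = 168 h. With dosing on Day 1, Day 7 is about 6 × 24 = 144 h and Day 9 about 8 × 24 = 192 h. The final on-treatment value is therefore normally the 96 h sample, or an end-of-trial sample taken early in its window. Three of the four scheduled samples (4, 24 and 48 h) do not determine the shift category when a later value exists. A peak at those times that has resolved appears in the listings and in the time-point minimum or maximum, but in no count of subjects by dose.

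**3. The hepatic AESI.** Protocol 5.2.6.1.4 makes values meeting the thresholds an alert with follow-up under the DILI checklist. Section 5.2.6.2.1 requires all AESIs on the CRF, and 5.2.6.2.2 requires reporting within 24 hours. None of these depends on an opinion of clinical relevance. A qualifying sample would therefore be absent from the AESI table only after an omission or misclassification at the site. SAP 7.8.1 describes nothing that would detect such an error.

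**4. Comparison with the ECG plan.** SAP 5.3.2 predefines numeric notable ECG findings and categories. SAP 7.8.4 flags the notable findings and tabulates the categorical endpoints. Protocol 4.1.5.1 blinds the central interval readers. Yet Protocol 1.4.3.3 calls the QT risk low. Laboratory data have no equivalent threshold table.

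**5. Scale.** The SRD part has 8 × 6 = 48 active and 8 × 2 = 16 placebo subjects. The effect of one subject, with exact (Clopper-Pearson) 95% intervals, is:

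- Dose group: 0/6 = 0% (0 to 45.9%) against 1/6 = 16.7% (0.4 to 64.1%).
- Pooled placebo: 0/16 = 0% (0 to 20.6%) against 1/16 = 6.3% (0.2 to 30.2%).
- All active: 0/48 = 0% (0 to 7.4%) against 1/48 = 2.1% (0.1 to 11.1%).

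For zero events the upper limit is 1 − 0.025^(1/n); for n = 6 this is 1 − 0.541 = 0.459.

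**The case against.** The strongest case for the plan is that objective information is kept and the choice is open. Minimum and maximum are tabulated per time point, so with six active subjects an extreme value, including a transient one, is visible without anyone's opinion. The trial is exploratory, tests no hypotheses and discloses its unblinded assessors. SAP 4 declares agreement with the protocol, which itself makes the investigator's view of relevance the criterion. Escalation does not wait for these tables: Protocol 3.1.1 requires laboratory results to at least 48 h at each Safety Review. Most of this stands.

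It rules out three stronger readings that a reader might infer:

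- **That every rule-based laboratory flag is switched off.** The sentence in SAP 7.8.2 is limited to clinically significant values; the reference-range displays remain. Counting the scheduled panels as unflagged would be wrong for the same reason.
- **That the hepatic AESI is at the investigator's discretion.** The clinical-relevance condition for ordinary laboratory AEs does not override the separate AESI duties.
- **That subjects go unmonitored.** The gap is in the analysis.

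Two further points are fair. The 1/6 and 1/16 steps apply to any binary outcome in this trial, so they show sensitivity, not the number of findings likely to be misclassified. The sponsor's laboratory standard, cited in SAP 7.8.2, is not available here and may add displays. It cannot, however, be assumed to restore rules that the SAP expressly declines to apply.

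What the objection does not supply is a threshold count by group. A maximum shows that at least one subject reached a value, but not how many did.

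**Conclusion.** The concern holds in a limited form. The SAP plans no objective, threshold-based frequency of marked laboratory abnormalities by dose against pooled placebo, and describes no programmed check of the numerically defined hepatic AESI. Where significance is assigned, it rests on people who know the treatment. One different classification shifts a dose-group rate by 16.7 percentage points and the pooled placebo rate by 6.3.

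This should be changed because the change is cheap and the laboratory risks are central to the protocol's own safety case. It does not undermine the trial.

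The conclusion rests on two assumptions. RPM membership is not listed, so the RPM is taken to be unblinded because the sponsor functions are and no blinded laboratory reviewer is described. The unseen laboratory standard is assumed not to add a threshold count. Neither the direction of any bias nor the number of findings affected can be estimated from the documents.

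**What to change.** 1. **SAP 7.8.1.** Programme the protocol's hepatic criteria (both arms, with the same-sample condition) on every post-dose sample. Use measured values and the site laboratory's ULN, because SAP 7.8.2 analyses normalised values and does not say whether multiples of ULN are preserved. Tabulate subjects by dose and pooled placebo (fed and fasted in the FE part), reconcile with the eCRF AESI flag and list any mismatch.
2. **SAP 7.8.2.** Replace the sentence restricting significant values to those named by the investigator or at the RPM, and the sentence declining standard rules. The new text should apply the sponsor's prespecified standard criteria to all post-dose on-treatment values, using the worst value rather than only the last, as a supplementary table by dose and pooled placebo. Keep the investigator's opinion of clinical significance and show it separately. The criteria are not in the documents, so the SAP should state or cite them and confirm that they suit healthy volunteers.

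The cost is SAP wording and one or two tables from data already collected. The downside is some flags with no clinical relevance, which the separate investigator column makes plain. The change supplements clinical judgement and leaves the primary endpoint as defined.

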7.8.3 Vital signs

The analysis of vital signs will be descriptive in nature. Descriptive statistics of vital signs over time and for the difference from baseline (see Section 6.7) will be provided.

Clinically relevant findings in vital signs data will be reported as baseline conditions (prior to first study drug administration) or as AEs (during the trial) if judged clinically relevant by the investigator, and will be analysed as such.

7.8.4 ECG

Abnormal findings will be reported as baseline conditions (prior to first study drug administration) or as AEs (during the trial) if judged clinically relevant by the investigator.

Descriptive analysis of ECG endpoints will be based on the TS. The evaluation of the relationship between plasma concentration and change in ECG endpoints (exposure-response analysis) will be based on the ECGPCS.

Listing of individual data

For all quantitative endpoints, listings of individual data will be shown in Appendix 16.2. For QTcB and RR, only listings will be provided. Occurrences of notable findings will be flagged.

Comments regarding the ECGs will be listed.

Categorical endpoints

For the categorical endpoints, frequency tables will be provided.

For all subjects with any notable finding in ECG intervals, a separate listing will be created as end-of-text display (based on the same display template as in Appendix 16.2), and the corresponding time profiles will be shown.

Quantitative endpoints

Descriptive statistics (N, mean, SD, min, median, max) will be provided for the changes from baseline over time of QTcF, HR, QT, PR and QRS. The time profiles of mean and SD for the changes from baseline on treatment will be displayed graphically by treatment group.

Exposure-response analysis

To analyse the relationship between changes from baseline in QTcF and HR and the time-matched plasma concentrations a random coefficient model will be applied to the ECGPCS, including placebo treated subjects. For a list of time points with scheduled ECG assessments and a time-matched plasma concentration, refer to [Table 6.7: 1](#).

For the handling of missing values, see [Section 6.6](#).

The remaining Section describes the analysis for QTcF only, however the same analysis will be performed for HR.

The response variable will be change from baseline in QTcF (Δ QTcF). The placebo subjects will be included in the analysis, setting their plasma concentrations to zero.

As a first step, it is investigated if there is a potential delayed or accelerated (e.g. due to metabolites) effect of the drug on QTcF. A general visual impression will be provided by overlaying time profiles of plasma concentrations and QTcF changes from baseline (Δ QTcF). These figures will be generated for each subject (presented in the Statistical Appendix of the CTR), as well as for means per treatment group (presented in the End-of-Text part of the CTR).

The relationship between BI 764122 plasma concentrations and QTcF changes from baseline will be investigated in an exploratory manner using a random coefficient model to estimate the difference in mean QTcF change from baseline between BI 764122 and placebo and its

90% confidence interval at the geometric mean of C_{max} for each dose. Additionally, the estimated overall slope with its 90% confidence interval will be provided. The used random coefficient model is based on a white paper from Garnett et. al. [R18-0143] (10) with $\Delta QTcF$ as response variable, centred baseline QTc and plasma concentration as continuous covariates, treatment and time as fixed categorical effects, and a random intercept and slope for each subject. For more details refer to [Additional Section 9.2](#).

For visualization, a scatterplot of the BI 764122 plasma concentration against the following individual QTcF values will be provided: For each subject on active treatment and each time point, subtract the mean value of all individual observed $\Delta QTcF$ values from the placebo group for this time point from the individual observed $\Delta QTcF$ value for this subject and time point. This results in estimates for “individual $\Delta\Delta QTcF$ ” values, which should only be used for plotting purposes. The corresponding regression line and its pointwise confidence bands as well as the geometric mean of C_{max} for each dose will additionally be displayed in the plot.

To check model assumptions, the conditional residuals will be plotted and presented in the Statistical Appendix of the CTR. In case of non-linearity or if there is evidence for a delayed effect, further models will be explored in order to better characterise the PK-ECG relationship (e.g. effect compartment models, non-linear models, etc.).

Appropriateness of heart rate correction methods of QT interval

To evaluate the appropriateness of the heart rate correction methods, the slope of the relationship of QTcF interval versus RR interval (values log-transformed using the natural logarithm) will be estimated by applying the random coefficient model described in [Section 9.1](#) using all time points. A scatterplot of $\ln(QTcF)$ vs $\ln(RR)$ including the overall regression line will be included in the Statistical Appendix of the CTR. The resulting (fixed effect) slope together with two-sided 95% confidence intervals will be included in the footnote for this plot.

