## FLOW CHART

Single rising dose (SRD) part:

Visit	Day	Planned time (relative to drug administration) [h:min]	Approximate clock time of actual day [h:min]	Event and comment	Safety laboratory	PK blood 	12-lead ECG	Continuous ECG monitoring	Vital signs (BP, PR)	Questioning for AEs and concomitant therapy 
1	-28 to -1			Screening (SCR) 	x					
2	-3 to -1	-72:00 to -24:00	08:00	Ambulatory visit	x 					x
	1	-1:30	06:30	Admission to trial site						
		-0:30	07:30	Allocation to treatment 	x 	x 				
		0:00	08:00	Drug administration						
		0:10	08:10			x				
		0:20	08:20			x				
		0:30	08:30			x				
		0:45	08:45			x				
		1:00	09:00			x 				
		1:30	09:30			x				
		2:00	10:00	240 mL fluid intake		x				
		3:00	11:00			x				
		4:00	12:00	240 mL fluid intake, thereafter lunch 	x	x				
		6:00	14:00			x				
		8:00	16:00	Snack (voluntary) 		x				
		10:00	18:00	Dinner 		x				
		12:00	20:00			x				
	2	24:00	08:00			x	x			
		34:00	18:00			x				
	3	48:00	08:00	Breakfast (voluntary)  , discharge from trial site	x	x				
	4	72:00	08:00	Ambulatory visit		x				
	5	96:00	08:00	Ambulatory visit	x	x				
	6	120:00	08:00	Ambulatory visit		x				
3	7 to 11			End of trial (EoT) examination 	x				x	x

1. Subject must be informed and written informed consent obtained prior to starting any screening procedures. Screening procedures include physical examination, check of vital signs, ECG, safety laboratory (including drug screening), demographics (including determination of body height and weight, smoking status and alcohol history), relevant medical history, concomitant therapy and review of inclusion/exclusion criteria.
2. The time is approximate; procedures are to be performed and completed within the 3 h prior to drug administration. Allocation to treatment may be performed at any time following enrolment but must be completed prior to (first) drug administration.
3. If several actions are indicated at the same time, the intake of meals will be the last action.
4. At the end of trial visit the EoT examination includes physical examination, body weight, vital signs, ECG, safety laboratory, recording of AEs, and concomitant therapies.
5. Only urine drug screening and alcohol breath test will be done at this time.

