6.7 BASELINE, TIME WINDOWS AND CALCULATED VISITS

In all analyses (except for analyses of ECG variables), the last available off-treatment value determined prior to the first dosing of trial medication of the respective treatment period will be defined as baseline. This means that a separate baseline is defined for each study treatment of the FE part. Off-treatment in this context means that a value measured within an on-treatment phase, as defined in [Table 6.1: 1](#), will not be used as baseline for any study treatment.

There will be a centralised evaluation of all 12-lead ECG recordings for the SRD part at the time points specified in [Table 6.7: 1](#):

Table 6.7: 1 Time schedule of 12-lead ECG recordings with centralised evaluation

Visit	Day	Planned time [hh:mm] (relative to respective drug administration)	Study phase
2	1	-00:30	Baseline
		00:10	On-treatment
		00:30	
		00:45	
		01:00	
		01:30	
		02:00	
		03:00	
		04:00	
		06:00	
		08:00	
	2	10:00	
		12:00	
	2	24:00	

Three triplicate ECGs will be recorded as the baseline before the first drug administration, but only the first ECG of each of the 3 triplicates will be evaluated. The baseline value of an ECG variable is defined as the mean of the transferred baseline ECG measurements prior to drug administration. At all other time points, 1 triplicate ECG will be recorded, but only the first ECG of the triplicate will be centrally evaluated.

For the exposure response analyses, pairs of ECG variables and corresponding plasma concentrations will be built using the same planned time points, e.g., the HR change from baseline and the plasma concentration measured at planned time 0:30 will build one pair. Note, there is a time-matched PK sample planned at each planned time of ECG recordings as outlined in Table 6.7: 1 above, see also Flow Chart in the CTP. Whether a time deviation between PK blood sampling time and corresponding ECG recording is too big for a reliable assessment and the pair has to be excluded from the analysis will be decided no later than at the RPM.

Time windows are defined in Section 6.1 of the CTP. Adherence to time windows will be checked at the RPM/DBLM.

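### The look for a delayed QTcF or heart-rate effect plots change from baseline without subtracting placebo, so time-of-day or meal changes shared with placebo can resemble or hide a delay (minor; exploratory figures only)

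*SAP*

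**What the plan says.** SAP 7.8.4 (Exposure-response analysis) makes timing the first question: "it is investigated if there is a potential delayed or accelerated (e.g. due to metabolites) effect of the drug on QTcF". The tool it names is a figure: "A general visual impression will be provided by overlaying time profiles of plasma concentrations and QTcF changes from baseline". On the level of display: "These figures will be generated for each subject (presented in the Statistical Appendix of the CTR), as well as for means per treatment group". The section is written for QTcF, "however the same analysis will be performed for HR".

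Change from baseline is defined through SAP 6.7: "The baseline value of an ECG variable is defined as the mean of the transferred baseline ECG measurements prior to drug administration". Three triplicates are recorded before dosing and the first ECG of each is read, so baseline is the mean of three pre-dose ECGs. It is not matched by clock time to the later readings.

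Placebo is subtracted in one place, the scatterplot of concentration against individual ΔΔQTcF. For each active subject and time point the instruction is to "subtract the mean value of all individual observed" placebo ΔQTcF values at that time. That plot has concentration on its horizontal axis, not time, and the SAP limits these individual values to plotting.

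The random coefficient model includes placebo subjects at concentration zero, with treatment and time as fixed categorical effects. After the residual plots, the SAP adds: "In case of non-linearity or if there is evidence for a delayed effect, further models will be explored".

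**The concern.** A delayed effect is one that appears after the concentration peak. To see it, the reader needs a response curve from which changes unrelated to drug have been removed. Change from a fasted, early-morning baseline does not do this.

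In the SRD Flow Chart dosing is at about 08:00. The 4 h entry reads "240 mL fluid intake, thereafter lunch", the snack is at 8 h and dinner at 10 h. Meals come last among the actions at a time point, so the 4 h ECG precedes lunch, while the centrally read ECGs at 6, 8, 10 and 12 h all follow at least one meal and fall in the afternoon or evening. A shared change there would recur in every dose group, so agreement between groups would not confirm a drug effect.

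Two errors are possible. A false impression of delay could start a search through effect-compartment or non-linear models. A masked delay could leave the direct-effect model in place, whose estimate is read at the geometric mean Cmax and would understate a delayed effect. Heart rate gets the same check, and Protocol 1.4.3.1 singles it out for close monitoring because of the dog telemetry findings.

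**Working it through.** The plan states no figure for this check, so there is none to reproduce. The check has four parts.

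**1. What each planned display controls for**

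| Display or analysis (SAP 7.8.4) | Time axis | Placebo control |
|---|---|---|
| Overlay, each subject | yes | none on the figure |
| Overlay, treatment-group means | yes | not subtracted; placebo is a separate group |
| Mean and SD change profiles by treatment group | yes | not subtracted; placebo shown as a group |
| Scatterplot of ΔΔQTcF on concentration | no | subtracted |
| Random coefficient model | fixed time effect | placebo subjects included |

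No planned display has both a time axis and a subtracted placebo.

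**2. Deterministic illustration**

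Inputs: the 13 on-treatment times of SAP Table 6.7: 1; half-life 3.3 h (Protocol 1.2.6, a prediction that the protocol says may be substantially exceeded). Assumptions: one-compartment oral profile with absorption rate 3/h; direct effect of E ms at Cmax; shared change A·exp(−½((t−6)/2)²) ms.

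The concentration peaks at the 1 h sample and at 6 h is 0.373 of its peak. Change from baseline is Δ(t) = E·C(t)/Cmax + shared(t); subtracting placebo leaves E·C(t)/Cmax.

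- E = 0, A = +5: Δ peaks at 6 h (5.0 ms). ΔΔ is flat.
- E = 5, A = +5: at 6 h, Δ = 5 × 0.373 + 5 = 6.9 ms, the peak. ΔΔ peaks at 1 h.
- E = 10, A = +5: Δ still peaks at 1 h (10.2 ms); A = +10 moves it to 6 h (13.7 ms).
- Truly delayed effect of 5 ms (assumed equilibration half-life 3 h), A = −5: Δ is 2.8 ms at 3 h and −0.1 ms at 6 h, while ΔΔ peaks at 4 h with 4.9 ms.

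A shared change can therefore imitate or hide a delay when it is about as large as the drug effect.

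**3. Simulation with a numerical stand-in**

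The SAP's check is visual, so a contrast replaced it: mean Δ at 6, 8, 10 and 12 h minus mean Δ at 0.5, 0.75, 1, 1.5 and 2 h (baseline cancels), two-sided 10% test, 6 active and 16 placebo. Assumed SDs were 8 ms within subject and 5 ms between subjects for the late change, so the contrast SD is √(64 × (1/4 + 1/5) + 25) = 7.3 ms. There were 20,000 runs per scenario.

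| Shared change, no drug effect | Active group alone signals | Active minus placebo signals | Placebo group alone shows the shift | Active signals and placebo does not |
|---|---|---|---|---|
| 3 ms | 22% | 10% | 47% | 12% |
| 5 ms | 42% | 10% | 83% | 7% |
| 8 ms | 74% | 10% | 99% | 0.5% |

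At a shared 5 ms, the active-alone rate ranges from 30% (SDs 10 and 7) to 68% (SDs 6 and 3). With a true late effect of +8 ms and a shared fall of 5 ms, detection is 23% for active alone and 72% after placebo subtraction. With no shared change it is 74% and 71%.

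**4. Price of subtracting placebo**

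Pooled placebo is 8 × 2 = 16. The standard-error ratio for a dose-group mean is √(1/6 + 1/16) / √(1/6) = 0.479 / 0.408 = 1.17. For an assumed SD of 8 ms, the standard error rises from 3.3 to 3.8 ms.

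**The case against.** The strongest reply is that the placebo control is already on show. Placebo is one pooled treatment group (SAP 6.1), and SAP 7.8.4 plots mean change profiles for QTcF and HR by treatment group, so the placebo curve is available at the same planned times. In the simulation the placebo group shows a shared 5 ms shift in 83% of runs, and discounting active signals that placebo also shows brings the false-signal rate from 42% to 7%. That largely stands for the group means. It is incomplete, because nothing tells the reader to make the comparison and the subject-level overlays carry no placebo curve.

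Second, the overlay does not settle the model alone. The sentence on further models follows the conditional residual plots, which come from a model with placebo and time effects. The analysis is described as exploratory. This stands and limits the consequence.

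Third, central ECG reading is done after the study (Protocol 5.2.4.1), and cardiac safety during the trial uses locally generated values. No escalation decision waits on these figures. This stands.

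Fourth, SAP 7.8.4 refers to an Additional Section 9.2 for model detail. That section is not in the supplied text, so further delay diagnostics there cannot be excluded.

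**Conclusion.** The point holds as a minor weakness of an exploratory display. The delay check uses change from a pre-dose, non-time-matched baseline without placebo subtraction, and a change shared with placebo, mainly at 6 to 12 h, can resemble or hide a delayed effect on QTcF or HR. What is exposed is the judgement on delay and, through it, the choice to explore further models.

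Two stronger readings do not follow. A reader might infer that the exposure-response results themselves are biased by time of day. The documents do not support this: the model has fixed time effects and placebo subjects, so its slope and Cmax estimates do not carry the shared change. A reader might also take 22% to 74% as the SAP's false-signal rate. Those rates come from a t-test that ignores the displayed placebo profile and stands in for a visual check with no stated rule. They also rest on assumed SDs and shifts, because the documents give none, and heart rate was not simulated. They show direction only.

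**What to change.** In SAP 7.8.4:

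- In the treatment-group overlays, plot the dose-group mean change minus the pooled-placebo mean change at the same planned time, with 90% CI, for QTcF and for HR.
- In the subject-level overlays, use the individual ΔΔ values already defined for the scatterplot (with the same derivation for HR), or add the pooled-placebo mean curve to each panel. The restriction of ΔΔ values to plotting already permits this and needs no change.
- State that a delayed or accelerated effect is judged on the placebo-corrected profiles, and keep the uncorrected overlays as supportive.

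The cost is a few words and a changed input to figures already planned, with no new data and no protocol amendment. The statistical price is the 17% larger standard error of the dose-group mean. In the simulation with no shared change, that was about 3 percentage points of detection.
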